**APPROXIMATE DURATION OF THE PROJECT:**

BEGINNING		TERMINATION	
Month	Year	Month	Year
August	2021	April	2024

**INVESTIGATION TYPE:**

Basic  Clinic  Sociomedic  Technology and Development

**GENERATES:**

Scientific Knowledge  Technology Application

**OBJECTIVE:**

Comprehension  Prevention  Diagnostic  Treatment  Rehabilitation

**RESEARCH LINE TO WHICH IT BELONGS:**

- Coronary disease
- Metabolic syndrome
- Primary systemic/pulmonary arterial hypertension
- Valve disease
- Cardiomyopathies and Chagas disease
- Biological systems: cellular, molecular and energy production
- Congenital heart disease
- Nephropathies
- Fabrication of intracardiac devices
- Environment and sociomedicine
- Other (Specify): Rheumatoid arthritis

CERTIFICATION ACCORDING TO PROJECT REQUIREMENTS. THE STUDY REQUIRES:

Subject Human		Animals (species, strain)		Components Electronics/Mechanical		Other	
Human cells		Bioassays		Radioactive material			
Consent Informed				Assent of Minors			

---

**ABSTRACT:**

The recent increase in autoimmune diseases in Western countries has led to the consideration of environmental factors as important disease triggers since the genetic basis has remained apparently constant in affected populations. For several years, diet has been seen as a modifying factor in rheumatoid arthritis (RA).

A high-fat diet changes the microbiome's structure even when there is an absence of obesity. However, it is also considered an important factor that promotes excessive accumulation of white adipose tissue (WAT) and systemic inflammation. For several decades, the participation of the intestinal microbiome in particular diet components' metabolism has been evaluated, and it has the potential to modify pro-inflammatory mediators or circulates anti-inflammatories. In the context of RA patients, the bacterium *Provetella copri* is found in a higher proportion in newly diagnosed patients. This bacterium generates a pro-inflammatory metabolite called trimethylamine N-oxide, derived from choline and carnitine, which is present in red meat, eggs, and dairy products. On the other hand, fruits and vegetables can modulate the intestinal microbiota through dietary fiber. The proportion of anti-inflammatory bacteria, such as *Faecalibacterium prausnitzii*, is found higher in vegetarian diets. It has been demonstrated that these bacteria are beneficial in RA patients associated with decreased inflammation.

For several years, it has been reported that the consumption of certain foods is associated with an increase or improvement in the symptoms of RA. However, a diet that combines several suggested strategies to reduce inflammation may represent a more significant intervention than simply including specific foods in the diet. Currently, the role of the plant-based diet in RA activity has not been fully elucidated.

Based on this evidence, this study aims to determine the decrease in RA activity associated with modifications of the plant-based diet. To carry out this protocol, we will evaluate women and men who are 18 years old or older with low, moderate, or severe RA activity. For the dietary intervention, at the beginning of the treatment, the RA patients will be evaluated anthropometrically (weight, height, body mass index, waist and hip circumference, waist-hip index, percentage of total fat, visceral fat, and percentage of muscle) and will have a baseline blood sample taken. The kilocalories consumed regularly will be calculated through a 24-hour recall to establish their personalized meal plan. A diet synthesis table will be created with the following macronutrient distribution: carbohydrates 57%, protein 18%, and lipids 25%. Subsequently, a distribution of the food will be made in an equivalent distribution table, complying with the kilocalories and the established percentage of macronutrients. The consumption of animal-origin foods will be reduced, replacing this protein with protein of vegetable origin. The intervention will be carried out for 15 days, and the menu will be modified after seven days of intervention following the same specifications.

At the end of the treatment, the patients will be evaluated under the same anthropometric conditions, and a blood sample will be collected for laboratory analysis. The DAS (Disease Activity Score) index, a scale that measures RA activity, will be used to determine the severity of the pathology. This scale takes into account the count of swollen and painful joints over 28 joints, the erythrocyte sedimentation rate (ESR), and the evaluation of the disease by the patient. The scale has a rating of 0.0 to 9.4.

**PROJECT OBJECTIVES:**

**Primary(s):**

**Secondary(s):**

To determine the decrease in rheumatoid arthritis (RA) activity associated with plant-based diet modifications

- To analyze the factors associated with changes in disease activity.
- To evaluate changes in acute phase reactants.
- To identify the adipokines related to the decrease or increase in disease activity tumor necrosis factor-alpha (TNF- $\alpha$ ), Interleukin 6 (IL-6), Leptin, and C-reactive protein (CRP).

## 1. TITLE.

The Effect of a Plant-based Diet on the Active Rheumatoid Arthritis Activity.

## 2. BACKGROUND.

The recent increase in autoimmune diseases in Western countries has been attributed to environmental factors, as the genetic basis of affected populations has remained constant. For several years, diet has been considered a modifying factor in rheumatoid arthritis (RA).

A high-fat diet can alter the microbiome structure, even in the absence of obesity. However, excessive accumulation of white adipose tissue (WAT) and systemic inflammation are also important factors that can alter the microbiome. WAT is considered an endocrine organ that releases a large number of pro-inflammatory mediators, such as TNF- $\alpha$ , IL-6, leptin, resistin, and CRP, which can have a major impact on T-cell responses and directly influence the inflammatory activity of autoimmune diseases (Manzel et al., 2014). The imbalance of these adipokines could explain the low-grade chronic systemic inflammation in obese subjects. Furthermore, upregulation of these factors leads to a chronic inflammatory state and contributes to metabolic dysfunction (Ouchi Noriyuki et al., 2011).

For several decades, the role of the intestinal microbiome in the metabolism of some diet components and its potential to modify circulating pro-inflammatory or anti-inflammatory mediators has been evaluated. In RA patients, the bacterium *Proteobacteria* is found in higher proportions in newly diagnosed patients. This bacterium produces a pro-inflammatory metabolite called trimethylamine N-oxide derived from choline and carnitine present in red meat, eggs, and dairy products (Scher et al., 2013). On the other hand, fruits and vegetables can modulate the intestinal microbiota through dietary fiber. The proportion of anti-inflammatory bacteria, such as *Faecalibacterium prausnitzii*, is higher in vegetarian diets. In the fecal flora, these bacteria have been found to be beneficial in RA patients associated with decreased inflammation (Haghighatdoost et al., 2017).

Early changes in the microbiota have been associated with changes in adipocytokine levels. Various studies have investigated the association between adiponectin levels and pro-inflammatory markers in several diseases. In RA patients, elevated local and systemic adiponectin levels have been observed in the presence of chronic inflammation. In vitro studies indicate that adiponectin has pro-inflammatory effects on chondrocytes and synovial fibroblasts (Fantuzzi, 2008). Furthermore, adiponectin production by adipocytes can be inhibited by pro-inflammatory factors, such as TNF and IL-6 (Berg & Scherer, 2005). Also, a correlation between high adiponectin and reduced inflammation has been observed in RA patients.

## 3. PROBLEM STATEMENT.

For several years, it has been suggested that certain foods may be associated with an increase or improvement in RA symptoms. However, combining several dietary strategies to reduce inflammation may represent a more effective intervention than simply incorporating specific foods. Currently, the role of a plant-based diet in RA activity has not been fully elucidated.

### 3.1. JUSTIFICATION.

In a clinical trial that aimed to examine the role of fecal flora in diet-induced improvement in RA patients, the findings showed an association between intestinal flora and disease activity, which may have implications for our understanding of how the diet can affect RA (Peltonen et al., 1994). On the other hand, a meta-analysis showed that individuals who followed a vegetarian diet for at least two years had low serum concentrations of C-reactive protein (CRP) and high concentrations of IL-6 compared to omnivores (Haghighatdoost et al., 2017). Therefore, evaluating in the short term how dietary modifications could influence disease activity could serve as an adjunct to standard therapy in the care of patients with disease activity, even those who are difficult to control.

### 3.2. RESEARCH QUESTION.

What is the influence of changing from a dietary regime daily to a plant-based diet for 14 days on active RA disease activity?

### 4. HYPOTHESIS.

- A plant-based diet modifies disease activity in patients with active RA.

### 5. METHOD.

The study population will consist of women or men aged 18 years or older with rheumatoid arthritis, including those with low, moderate, or severe disease activity.

#### 5.1 Preparation of the plant-based diet

Diet:

The food plan will take into consideration all the data obtained during the nutritional intervention. The total number of calories required by each patient will be estimated using the average calories obtained from the 24-hour recall and the Harris-Benedict formula (appointment). A synthetic diet chart will be created with the following macronutrient distribution: carbohydrates 57%, protein 18%, and lipids 25%. The food will then be distributed in an equivalent distribution table, complying with the established percentage of macronutrients and calorie requirements. In this protocol, the consumption of animal-based foods will be reduced and substituted with plant-based protein. The intervention will be carried out for 15 days. After seven days of intervention, the menu will be modified following the same specifications, resulting in two weekly menus. Patients will keep a food diary to track the food consumed (servings) on a daily basis. The diary will be reported daily to the responsible nutritionists by telephone and/or text message.

Diet overview:

The plant-based diet will consist of a normal diet with a macronutrient distribution of carbohydrates 57%, protein 18%, and lipids 25%. The diet will be divided into four meals: breakfast, morning or evening snack, lunch, and dinner, and will be consumed orally.

#### 5.2. STUDY DESIGN

- Type and general design of the study
- RA patients with disease activity and modification with dietary intervention in the determined time of 14 days.
- According to the interference of the variables to be analyzed: Intervention
- According to the information capture period: Prospective
- According to the evolution of the study: Longitudinal
- According to the comparison of the populations: Analytical

#### 5.3. DESCRIPTION OF THE STUDY POPULATION:

● 5.3.1. Target population:

- RA patients with disease activity to any degree.

● 5.3.2. Eligible population

- Patients attending the Rheumatology consultation at the National Institute of Cardiology Ignacio Chávez

● 5.3.3. Inclusion criteria

- People  $\geq 18$  years old
- Established diagnosis of RA according to the criteria ACR 1987 or ACR/EULAR 2010
- Disease activity according to DAS 28 (defined as everyone  $> 2.6$ ).

5.3.4. Exclusion criteria

- Systemic autoimmune overlap syndrome (with the exception of: fibromyalgia, thyroid disease, DM1, Sjögren's syndrome, and antiphospholipid syndrome)
- Patients treated with coumarins.
- Cancer patients, chronic hepatitis, HIV, pregnancy
- Weight changes associated with diet in the last 6 months

5.3.5. Elimination criteria

- Patients who have died in the process before finishing the sampling.
- Patients who have suspended the intervention
- Lack of adherence to diet  $< 80\%$
- Loss to follow-up
- COVID infection requiring hospitalization (moderate-severe)

5.4. SAMPLE SIZE.

Convenience sampling will be carried out on patients at the National Institute of Cardiology who agree to participate, with a total n of 28.

5.5. SPECIFICATION OF DEPENDENT AND INDEPENDENT VARIABLE (S).

Variable	Measurement Level	Concept
DAS28 initial and post intervention	Continuous quantitative	Remission: <or equal to 2.6 (assess valid only in post-intervention), mild:> 2.6- <3.2, moderate:> or equal to 3.2- <or = 5.1, severe:> 5.1
CDAlinitial and post intervention	Continuous quantitative	<or equal 2.8, remission,> 2.8-10: mild activity, moderate> 10-22: moderate activity,> 22 serious activity
SDAI initial and post intervention	Continuous quantitative	<or equal to 3.3: remission, 3.3-11 mild activity,> 11-26 moderate activity,> 26 serious activity
PCR	Continuous quantitative	
Globular Sedimentation Volume (GSV)	Continuous quantitative	
IL-6	Continuous quantitative	
Adiponectin	Continuous quantitative	Protein produced mainly by adipocytes that belongs to the adipokine family.
Aggregate comorbidities (DM, HAS, Hypothyroidism, Dandslipidemia, smoking)	Nominal qualitativ.	Concomitant diseases added to patients, determined as present or not.
Age of diagnosis	Discrete quantitative.	Determined in completed years
Age of the patient	Discrete quantitative.	Determined in completed years
Gender	Nominal qualitativ.	Dichotomous in feminine or masculine
BMI	Continuous quantitative	Determination estimated according to weight and height, standardized by degrees in overweight (25-29.9), obesity grade I (30-34.9), grade II (35-40) and morbid obesity (> 40)
% total body fat	Continuous quantitative	Measurement established by bioimpedance determined by weighing machine TANITA
% visceral fat	Continuous quantitative	Measurement established by bioimpedance determined by weighing machine TANITA
% muscle / water	Continuous quantitative	Measurement established by bioimpedance determined by weighing machine TANITA
Morning stiffness	Nominal qualitativ.	Patient's perception of gelling phenomenon that improves with physical activity over a period of time.
#Swollen joints	Discrete quantitative.	Assessment established by the physician upon examination of the patients, without dependent relationship with painful joints.
#Painful joints	Discrete quantitative.	Patient referency to palpation on physical examination of pain joints
Fatigue	Qualitative ordinal.	Determinant as mild, moderate or severe for the daily situation manifested by the patient
Basal treatment	Qualitative ordinal.	Any DMARD, glucocorticoid, NSAID or supplement.

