**STATISTICAL ANALYSIS PLAN**

Spreadsheet databases will be created using the Excel program. The Kolmogorov-Smirnov test will be used to assess variable distribution. Proportions and percentages will be used to describe dichotomous, nominal, and ordinal variables, while means with standard deviation or medians with interquartile ranges will be used to describe dimensional variables, depending on the type of distribution.

To compare differences between two independent groups, appropriate statistical tests (Fisher's exact test or chi-square test for discrete variables, Student's t-test or Mann-Whitney test for continuous variables) will be used. For dependent variables, the paired T-test or the Wilcoxon rank sum will be used. If analysis of 3 or more groups is required, the Kruskal-Wallis test or one-way ANOVA will be used.

Associations will be explored using Spearman or Pearson's rho coefficients, as appropriate. All analyses will be conducted using two-sided testing, with significance set at P < 0.05.

For statistical analysis, the GraphPad Prism version 6.0 (GraphPad Inc., San Diego, CA) and IBM SPSS Statistics program for macOS, version 25 (IBM, Armonk, NY) will be used.

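### Section 5.3.5 eliminates enrolled patients who suspend the diet or adhere below 80%, so the uncontrolled before/after DAS28 comparison describes adherent completers only and is biased if stopping is related to response

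*Protocol*

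**What the plan says.** Section 5.3.5 of the protocol sets out elimination criteria separately from the inclusion criteria (5.3.3) and exclusion criteria (5.3.4). Its items can only occur after enrolment. Two depend on how the patient behaves during the diet: "Patients who have suspended the intervention" and "Lack of adherence to diet", the latter with a threshold of 80%. Death, "Loss to follow-up" and hospitalisation for COVID are also listed but are not part of this point.

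The Project Objectives state the aim as "To determine the decrease in rheumatoid arthritis (RA) activity associated with plant-based diet modifications", and Section 4 frames the hypothesis for patients with active RA. Section 5.2 describes one dietary intervention, and no control group is defined anywhere. Section 5.4 describes a convenience sample of patients "who agree to participate, with a total n of 28", without a power calculation or dropout rate.

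The Statistical Analysis Plan section says: "For dependent variables, the paired T-test or the Wilcoxon rank sum will be used", two-sided at 0.05. It gives no analysis of all enrolled patients and no handling of a missing final DAS28.

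Two other passages bear on the remedy. The Abstract says: "At the end of the treatment, the patients will be evaluated under the same anthropometric conditions, and a blood sample will be collected". On the food diary, Section 5.1 says: "The diary will be reported daily to the responsible nutritionists by telephone and/or text message".

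**The concern.** Suspension and poor adherence are known only after treatment has begun, and both may depend on how the patient is responding. Removing patients on those grounds changes the question from what happens to patients with active RA who are put on the diet to what happens to those who stayed on it. The second question is legitimate, but it concerns a selected group and should not supply the only result.

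Patients who see no benefit might stop or slacken more often. That is plausible, though the protocol does not document it. The retained patients would then show a mean decrease in DAS28 even if the diet did nothing. In a single-group design nothing offsets or reveals this, and the reader cannot separate the diet's effect from the effect of who was left in. The rule also gives up outcomes that could probably still be measured, since patients are in daily contact with the nutritionists and a final evaluation is planned.

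**Working it through.** **The plan's own figure.** The only number is n = 28, a convenience sample with no effect size, SD or dropout rate behind it. There is nothing to reproduce.

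**Inputs from the protocol:** 28 patients; paired comparison; two-sided 5% test.

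**Assumed, because the protocol gives neither:** the share eliminated, f, from 10% to 30%; and the correlation r between staying in and DAS28 improvement, from −0.3 to 0.7.

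**Model.** Improvement and propensity to stay are bivariate standard normal with correlation r. True mean change is zero, and the fraction f with the lowest propensity is removed. Results are in SDs of the DAS28 change.

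**Bias among those retained** = r × φ(z_f) / (1 − f), where z_f is the f-quantile and φ the standard normal density. For f = 0.2, φ(z_f) = 0.280, so 0.5 × 0.280 / 0.8 = 0.175 SD toward a decrease.

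**Rejection rate** of the paired t-test (simulation, 200,000 trials per setting, 28 enrolled):

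| f | r | Bias (SD) | Two-sided rejection |
|---|---|---|---|
| 10% | 0.3 | 0.058 | 5.9% |
| 20% | 0 | 0 | 5.0% |
| 20% | 0.3 | 0.105 | 7.7% |
| 20% | 0.5 | 0.175 | 13.2% |
| 20% | 0.7 | 0.245 | 22.9% |
| 30% | 0.7 | 0.348 | 38.4% |

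A repeat with 40,000 trials gave 13.0% for the 20%, r = 0.5 case and 38.8% for the last row. With r = −0.3 and 20% eliminated, the bias is 0.105 SD the other way, and a false decrease is declared in 0.7% of trials instead of 2.5%.

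**If 28 means evaluable.** About 28 / 0.8 = 35 would be enrolled. With r = 0.5 the bias is still 0.175 SD and rejection is 15.2%.

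**Power.** The change detectable with 80% power (noncentral t) is 0.549 SD at n = 28. If 28 means enrolled, 28 × 0.8 ≈ 22 remain and it becomes 0.626 SD.

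**Does measuring those who stop help?** At f = 0.2 and r = 0.5, the eliminated patients' mean improvement is −0.5 × 0.280 / 0.2 = −0.70 SD. Suppose a final DAS28 is obtained at random from some of them:

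- from half: (0.8 × 0.175 − 0.1 × 0.70) / 0.9 = 0.078 SD, rejection 6.8%;
- from 75%: (0.140 − 0.105) / 0.95 = 0.037 SD, rejection 5.4%;
- from all: 0.140 − 0.140 = 0, rejection 5.1%.

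**Does imputation alone help?** Assigning every eliminated patient no change leaves 0.8 × 0.175 = 0.140 SD and 13.0%. Assigning a worsening of 0.25 SD leaves 0.140 − 0.2 × 0.25 = 0.09 SD and 7.5%; 0.5 SD leaves 0.04 SD and 5.2%; 0.7 SD leaves 0 and 5.2%. No-change imputation is therefore not a safeguard by itself.

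**The case against.** The strongest reply has four parts.

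- **Interpretation.** Section 5.3.5 does not say that data are dropped or that no final DAS28 is taken, and a separate SAP could define an all-enrolled set. Removal is nevertheless the natural reading of a post-enrolment list kept apart from the exclusion criteria, and the protocol's own statistical section does not counter it. If patients who stop are not measured, no later SAP can recover their values.
- **Target.** The objective and the research question in Section 3.2 can be read as the effect of eating the diet, for which an adherent set is relevant. That is granted, and it is a reason to keep that set, not to make it the only one.
- **Size.** The magnitude is wholly assumed. The intervention lasts about two weeks with daily contact, so attrition may be small; at 10% and r = 0.3 the effect is negligible. This stands: the figures show what could happen, not what will.
- **Remedy.** It was tested only with no true effect. With a true effect, including patients who stopped estimates a different and usually smaller quantity. Nor does the planned end-of-treatment evaluation expressly cover someone who stopped early. Both points stand.

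Two smaller points also stand. The use of the food diary to judge the 80% threshold is inferred from Section 5.1, not stated. An all-measured analysis and its sensitivity analysis would also take in patients affected by the other elimination criteria.

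**Conclusion.** The concern holds and should be fixed. It is certain that the protocol eliminates patients on two post-baseline, behaviour-dependent grounds and offers no all-enrolled analysis. The direction and size of any bias cannot be determined from the protocol. Under the assumed ranges (10–30% eliminated, r from 0.3 to 0.7, no true effect, 28 enrolled) the bias is 0.06–0.35 SD toward a decrease and the nominal 5% test rejects in about 6–38% of trials. It vanishes at r = 0 and reverses for negative r. The loss of power, from 0.55 to 0.63 SD detectable at 20% elimination, arises only if 28 means enrolled; the selection problem arises either way.

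**What to change.** 1. In Section 5.3.5, remove suspension and adherence below 80% as reasons for elimination from the primary analysis.
2. Obtain the end-of-intervention DAS28 from every enrolled patient, and say explicitly that this includes those who stop the diet.
3. Make the primary paired analysis all enrolled patients with a baseline and a final DAS28, whatever their adherence. State how the remaining elimination criteria, such as COVID hospitalisation, apply to it.
4. Keep patients with at least 80% adherence as a labelled secondary analysis. Word the criterion as adherence below 80%, since the printed line literally refers to a lack of adherence below 80%, and say how adherence is measured.
5. For patients without a final DAS28, report numbers and reasons. Run a sensitivity analysis from no change to increasing worsening (for example 0, 0.25, 0.5, 0.7 and 1.0 SD), and state where the conclusion changes. Do not rely on no-change imputation alone.
6. In Section 5.4, state whether 28 means enrolled or evaluable.

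The cost is rewording of Sections 5.3.5, 5.4 and the statistical section, plus a final evaluation for the patients who stop. The estimated decrease may be somewhat smaller. The change removes only this selection: regression to the mean (entry requires DAS28 above 2.6) and expectation effects remain in an uncontrolled design, so the 5% error rate is restored with respect to this problem alone.

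### No criterion covers a recent or concurrent change in antirheumatic treatment, and no such change is named for recording, so this one-group before/after comparison would count its effect in the diet result.

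*Protocol*

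**What the plan says.** **Eligibility and elimination.** Inclusion (5.3.3) requires age 18 or over, an RA diagnosis and DAS28 above 2.6. Exclusion (5.3.4) has one drug criterion, "Patients treated with coumarins", which is not about antirheumatic treatment. It also has one stability condition, on diet-related weight change in the previous 6 months. Elimination (5.3.5) lists death, "Patients who have suspended the intervention", diet adherence below 80%, loss to follow-up and COVID requiring hospitalisation. None of the three lists mentions a change in antirheumatic treatment.

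**Recording.** The variable table in section 5.5 has one treatment item, basal treatment: "Any DMARD, glucocorticoid, NSAID or supplement". It has no entry for a change in treatment or for the date of one.

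**Design and analysis.** Section 5.2 describes "RA patients with disease activity and modification with dietary intervention in the determined time of 14 days" and defines no comparator. The statistical analysis plan section gives the before/after test: "For dependent variables, the paired T-test or the Wilcoxon rank sum will be used".

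**Setting and aims.** Section 5.3.2 draws on "Patients attending the Rheumatology consultation" at one institute. Section 3.1 says that the approach "could serve as an adjunct to standard therapy in the care of patients with disease activity, even those who are difficult to control". A secondary objective is "To analyze the factors associated with changes in disease activity".

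**The concern.** The primary objective is the fall in disease activity associated with the diet. With one group measured twice, whatever else moves DAS28 between the two visits is part of the estimate. Antirheumatic drugs are meant to act on that outcome. A drug started or increased shortly before baseline, or during the diet, could lower DAS28 and look like a diet effect. One reduced or stopped could raise DAS28 and hide a diet effect. In a controlled trial such changes would tend to balance between arms, but here nothing balances them.

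The protocol screens for a recent change in weight due to diet, yet has no counterpart for drugs. If a change is not recorded, no later analysis plan can recover it, and it cannot be examined under the secondary objective on factors associated with changes in activity.

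**Working it through.** **1. The text.** All three lists of criteria were read for any condition on DMARDs, glucocorticoids or NSAIDs. There is none. A patient whose treatment was changed just before baseline is eligible as written, and a patient whose treatment is changed during the diet stays in the analysis with no stated record of the change.

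**2. Is there a comparator?** The statistical analysis plan section also names tests for two independent groups and for three or more groups. No control arm, allocation or randomisation is described anywhere, so the diet effect rests on the before/after change.

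**3. Size, as an illustration only.** The protocol gives no effect size, SD or power, so there is no figure of its own to reproduce.

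- From the protocol: n = 28 (5.4); two-sided test at 0.05.
- Assumed, not in the protocol: SD of DAS28 change 0.8 to 1.2; drug effect d = 0.6 to 1.2 points within the interval; share of patients who change p = 5%, 10% or 20%; true diet effect 0.

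Count a fall as positive. A false fall is t > 2.052 (the 97.5% point on 27 df), which has probability 2.5% with no diet effect and no drug change.

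*All changes lower DAS28.* Mean = p·d; variance = SD² + p(1−p)d²; non-centrality = √28 × mean / √variance.

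- Low end at p = 10%: d = 0.6, SD = 1.2. Mean 0.06; variance 1.44 + 0.09 × 0.36 = 1.4724, root 1.213; non-centrality 0.262; false fall 4.4%.
- High end at p = 10%: d = 1.2, SD = 0.8. Mean 0.12; variance 0.64 + 0.09 × 1.44 = 0.7696, root 0.877; non-centrality 0.724; false fall 10.4%.

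*Three quarters of changes lower DAS28, one quarter raise it.* Mean = 0.5·p·d; variance = SD² + p·d² − mean².

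*Even split.* The mean is 0, so the false-fall rate stays at 2.5%.

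| Share changing | All lower DAS28 | Three quarters lower it | Even split |
|---|---|---|---|
| 5% | 3.3%-5.5% | 2.9%-3.8% | 2.5% |
| 10% | 4.4%-10.4% | 3.3%-5.3% | 2.5% |
| 20% | 7.2%-25.9% | 4.4%-9.4% | 2.5% |

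**4. Masking.** Assume a true diet effect of 0.5 points and that all changes raise DAS28, so mean = 0.5 − p·d with the one-direction variance above. Power is 57%-89% with no changes, 45%-84% at 5%, 34%-78% at 10% and 18%-64% at 20%.

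**5. Does excluding the changers solve it?** Not by itself. A change during the diet comes after baseline and may be driven by disease activity. Simulation with no diet or drug effect dropped the patients highest on a trait correlated 0.3 to 0.5 with worsening. Dropping 10% shifted the mean 0.05 to 0.12 points towards improvement, with a false-fall rate of 4.7%-6.9%. Dropping 20% shifted it 0.09 to 0.21 points, with a rate of 7.0%-12.8%. A variant that dropped exactly 3 or 6 of the 28 gave 4.9%-7.6% and 7.4%-14.0%.

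**The case against.** **Nothing shows that treatment changes occur.** This stands. Section 3.1 describes a possible future use of the diet and sets no rule for trial patients. Section 5.3.2 names a clinic and does not say that entry coincides with a treatment decision. A reader might infer that treatment is being adjusted in these patients. The protocol does not say so. Changes around entry are plausible in active disease, and no more than that.

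**Recording may be adequate.** This stands in part. A reader might infer that treatment is recorded only once, because the basal treatment item lacks the initial and post-intervention label that DAS28 carries. That does not follow: acute phase reactants have no such label either, although a secondary objective is to evaluate their change. What can be said is that a change and its date are not named. The eligibility gap is the firmer half of the point.

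**The figures are assumed and the interval is short.** Both are correct. The upper values need every change to act in one direction and a 1.2-point drug effect within about two weeks. The short interval limits changes during the diet, but it does not remove the continuing effect of a drug changed just before baseline.

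**The root weakness is the missing comparator.** This is fair. The point is one consequence of that design and should not be counted at full weight alongside it. It has its own inexpensive remedy, however, and eligibility and data collection belong in the protocol, so it cannot be left to a separate analysis plan.

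**Conclusion.** The point holds as a gap in the criteria and in what is named for recording. As written, the plan admits patients with a fresh change in antirheumatic treatment and would count its effect in the DAS28 change attributed to the diet, in either direction.

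The stronger claim, that the trial's result will be biased or that the bias has a known size, is not supported. Under the stated assumptions the distortion is small if few patients change or if directions cancel. It becomes material only if about 10% to 20% change, mostly one way. Without a record, no reader could tell which case applies. The change should be made, but it is not a critical defect. The gap in the text is certain and its effect is unknown.

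**What to change.** - Add an eligibility condition that background antirheumatic treatment was unchanged for a period before baseline. The investigators set the period, and the condition places no restriction on treatment during the diet.
- Record at both visits the current antirheumatic treatment and the date of its last change.
- State that a treatment change alone is not a reason to remove a patient from the primary DAS28 analysis. The existing elimination list in 5.3.5 is a separate matter and is not altered by this.
- Report how many patients changed treatment and in which direction.
- Label any analysis without those patients as supportive only, and state its risk of selection bias. That bias can be about as large as the one being probed.

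The cost is one eligibility line, two data fields and a short report of changes, with slightly slower recruitment. The fix does not replace a comparator or remove regression to the mean.
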